9.4	Safety 12-Lead Electrocardiogram.....	32
9.5	Concomitant Medications.....	33
9.6	Extent of Exposure	33
9.7	Other Safety Assessments	33
10	References	34
	APPENDIX A: LIST OF TABLES, LISTINGS, AND FIGURES	35

LIST OF ABBREVIATIONS

λ_z	terminal elimination rate constant
$Ae_{urine(0-24)}$	urinary recovery between 0 and 24 hours
$Ae_{urine(0-72)}$	urinary recovery between 0 and 72 hours
$Ae_{urine(24-48)}$	urinary recovery between 24 and 48 hours
$Ae_{urine(48-72)}$	urinary recovery between 48 and 72 hours
$Ae_{feces(0-24)}$	fecal recovery between 0 and 24 hours
$Ae_{feces(0-72)}$	fecal recovery between 0 and 72 hours
$Ae_{feces(24-48)}$	fecal recovery between 24 and 48 hours
$Ae_{feces(48-72)}$	fecal recovery between 48 and 72 hours
AE	adverse event
AIC	Akaike's information criterion
AUC	area under the plasma concentration-time curve
AUC_{0-24}	area under the plasma concentration-time curve from time 0 to 24 hours
AUC_{0-48}	area under the plasma concentration-time curve from time 0 to 48 hours
AUC_{0-72}	area under the plasma concentration-time curve from time 0 to 72 hours
AUC_{0-inf}	area under the plasma concentration-time curve from time 0 extrapolated to infinity
AUC_{0-last}	area under the plasma concentration-time curve from time 0 extrapolated to the last observed concentration
AUC_{24-48}	area under the plasma concentration-time curve from time 24 to 48 hours
AUC_{48-72}	area under the plasma concentration-time curve from time 48 to 72 hours
AUC_{ext}	percentage of AUC_{0-inf} obtained by extrapolation
BQL	below the quantitation limit
CI	confidence interval
CL/F	apparent clearance following extravascular administration
$CL_{r(0-24)}$	renal clearance from time 0 to 24 hours
$CL_{r(0-72)}$	renal clearance from time 0 to 72 hours
$CL_{r(24-48)}$	renal clearance from 24 to 48 hours
$CL_{r(48-72)}$	renal clearance from 48 to 72 hours
C_{max}	maximum observed plasma concentration
CRU	clinical research unit
C_{feces}	concentration of drug in feces
C_{urine}	concentration of drug in urine
CV%	percent coefficient of variation
ddQTcF	time-matched, placebo-corrected, baseline-adjusted QTcF

dQTcF	baseline-adjusted QTcF
ECG	electrocardiogram
eCRF	electronic case report form
E _{max}	maximum effect
HR	heart rate
LLOQ	lower limit of quantitation
MDGH	Medicines Development for Global Health
MedDRA	Medical Dictionary for Regulatory Activities
msec	millisecond(s)
n	number
PD	pharmacodynamic(s)
PK	pharmacokinetic(s)
PT	preferred term
QTc	corrected QT interval
QTcB	QT interval corrected by Bazett's formula
QTcF	QT interval corrected by Fridericia's formula
QTcI	QT interval with individual correction
SAP	statistical analysis plan
SD	standard deviation
SOC	system organ class
t _{1/2}	terminal elimination half-life
TEAE	treatment-emergent adverse event
T _{max}	time to the maximum observed plasma concentration
U _{max}	time of maximal ddQTcF
V _d /F	apparent volume of distribution following extravascular administration
V _{urine}	urine volume
W _{feces}	fecal mass

1 INTRODUCTION

This statistical analysis plan (SAP) describes the statistical analysis methods and data presentation to be used for the analysis and summarization of pharmacokinetic (PK) and safety data from Protocol MDGH-MOX-1008 with Spaulding Clinical Research, LLC responsible for the analysis and presentation of the PK and safety data. In addition, the primary and exploratory endpoints detailing the pharmacodynamic (PD) analysis of electrocardiograms (ECGs) will be described in this analysis plan, with Mason Cardiac Safety Consultation responsible for the analysis and presentation of these data.

The analysis plan will be finalized prior to database lock. Any changes made after finalization of the analysis plan will be documented. Related documents are the study protocol and electronic case report forms (eCRFs).

2 OBJECTIVES AND ENDPOINTS

2.1 Primary Objective

The primary objective is to analyze the effect of a single oral dose of moxidectin on the QT interval associated with plasma moxidectin concentrations.

2.2 Secondary Objective

The secondary objective is to assess the safety and PK of a single oral dose of moxidectin.

2.3 Exploratory Objectives

The exploratory objectives are:

- To gain preliminary information in humans on the metabolism and excretion of moxidectin;
- To evaluate the baseline-corrected changes in other ECG and cardiovascular parameters; and
- To evaluate the ECG morphologic changes related to cardiac repolarization (ST segment and T waves).

2.4 Endpoints

2.4.1 Pharmacokinetic Endpoints

The plasma PK parameters of moxidectin will be determined from the concentration-time profiles for all evaluable subjects. Actual sampling times, rather than scheduled sampling times, will be used in all computations involving sampling times. The following plasma PK parameters will be estimated using noncompartmental parameters, unless otherwise specified:

1. AUC_{0-last} – area under the plasma concentration-time curve (AUC) from time 0 extrapolated to the last observed concentration;
2. AUC_{0-inf} – AUC from time 0 extrapolated to infinity;
3. AUC_{ext} – percentage of AUC_{0-inf} obtained by extrapolation (a diagnostic parameter calculated and listed in the data listing, but not included in the descriptive statistics);
4. AUC_{0-24} – AUC from time 0 to 24 hours;
5. AUC_{0-48} – AUC from time 0 to 48 hours;
6. AUC_{0-72} – AUC from time 0 to 72 hours;
7. AUC_{24-48} – AUC from time 24 to 48 hours;
8. AUC_{48-72} – AUC from time 48 to 72 hours;
9. C_{max} – maximum observed plasma concentration;
10. T_{max} – time to C_{max} ;
11. $t_{1/2}$ – terminal elimination half-life;
12. λ_z – terminal elimination rate constant;
13. CL/F – apparent clearance following extravascular administration;

14. V_d/F – apparent volume of distribution following extravascular administration.

In addition, exploratory endpoints include descriptions of metabolite concentrations over time for analytes in plasma, urine, and feces and metabolite to parent (molar equivalents) ratios over time for analytes in plasma and urine. The following parameters will be calculated for urine:

1. $Ae_{urine(0-72)}$ – urinary recovery between 0 and 72 hours;
2. $Ae_{urine(0-24)}$ – urinary recovery between 0 and 24 hours;
3. $Ae_{urine(24-48)}$ – urinary recovery between 24 and 48 hours;
4. $Ae_{urine(48-72)}$ – urinary recovery between 48 and 72 hours;
5. $CL_{r(0-72)}$ – renal clearance from time 0 to 72 hours;
6. $CL_{r(0-24)}$ – renal clearance from time 0 to 24 hours;
7. $CL_{r(24-48)}$ – renal clearance from 24 to 48 hours;
8. $CL_{r(48-72)}$ – renal clearance from 48 to 72 hours.

The following parameters will be calculated for feces:

1. $Ae_{feces(0-72)}$ – fecal recovery between 0 and 72 hours;
2. $Ae_{feces(0-24)}$ – fecal recovery between 0 and 24 hours;
3. $Ae_{feces(24-48)}$ – fecal recovery between 24 and 48 hours;
4. $Ae_{feces(48-72)}$ – fecal recovery between 48 and 72 hours.

The PK endpoints are considered secondary study endpoints. The main PK parameters of interest in this study are the cumulative and pre-specified time-window AUCs for moxidectin concentrations in plasma.

2.4.2 Pharmacodynamic Endpoints

The PD endpoints are calculated from the mean of the triplicate continuous 12-lead ECG data as:

1. $dQTcF$ – baseline-adjusted QT interval corrected by Fridericia's formula ($QTcF$);
2. $ddQTcF$ – time-matched, placebo-corrected, baseline-adjusted $QTcF$, which is calculated as the $dQTcF$ minus the time-matched mean $dQTcF$ of all placebo subjects at each postdose time point ($ddQTcF=[dQTcF(\text{active dose groups})-\text{mean } dQTcF(\text{placebo})]$);

The primary study endpoint is the $dQTcF$ matched to the plasma concentration of moxidectin collected at the same time point.

Analogous-derived exploratory endpoints are also calculated for heart rate (HR), and duration of PR, RR, and QRS interval parameters.

The ECG morphologic changes data are also considered an exploratory endpoint.

2.4.3 Safety and Tolerability Endpoints

The safety endpoints are:

1. Monitoring and reporting of adverse events (AEs);
2. Vital sign measurements;
3. Clinical laboratory test results (hematology, serum chemistry, urinalysis);
4. 12-lead safety ECG results;
5. Physical examination findings.

Secondary study endpoints include AEs, clinical laboratory test results, vital sign measurement, safety 12-lead ECG results, and physical examination findings.

3 STUDY DESIGN

3.1 Number of Subjects

There will be 60 generally healthy male subjects between 18 and 50 years old enrolled in the study.

3.2 Sample Size Considerations

The sample size of 60 subjects (10 subjects each in 6 treatment groups) is considered adequate to explore the effects of moxidectin on the corrected QT interval (QTc), as this design will yield 900 QTc-PK pairs in total. Additional subjects may be enrolled as alternates in this study should a subject choose to withdraw consent before study drug administration. Alternate subjects will remain in the clinical research unit (CRU) from Check-in until all subjects due to be dosed have completed dosing. Subjects who withdraw after dosing will not be replaced.

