3.3 Study Design

This is a randomized, single-center, double-blind, placebo-controlled, parallel-group study in which healthy male subjects will be randomly assigned to one of the following treatments:

- Treatment 1: moxidectin 4 mg (n = 10)
- Treatment 2: moxidectin 8 mg (n = 10)
- Treatment 3: moxidectin 16 mg (n = 10)
- Treatment 4: moxidectin 24 mg (n = 10)
- Treatment 5: moxidectin 36 mg (n = 10)
- Treatment 6: matching placebo (n = 10)

Subjects will be screened for eligibility up to 28 days before randomization. Subjects who meet all of the inclusion and none of the exclusion criteria will be admitted to the CRU on Day -1 (not less than 12 hours before scheduled dosing). Subjects will remain in the CRU for at least 72 hours after dosing and will return to the CRU for further assessment on Days 8, 15, and 22, and Week 12. At Week 8, subjects will be contacted via telephone for recording of AEs and concomitant medication use.

Randomized subjects will be assigned unique subject numbers in sequential order based on their order of qualification. Randomization will take place before dosing on Day 1, with equal random assignment to each treatment. Subjects are considered as enrolled once randomized.

The duration of participation in the study for each subject will be up to approximately 112 days, including Screening.

For purposes of statistical analysis, this study is divided into 2 study periods:

- Period 1: Commences at Screening and will finish on Day 22. The study blind will be maintained during this study period. After the last subject has completed the study through Period 1, the blind will be broken and the data from Period 1 will be analyzed.
- Period 2: Runs from Day 23 to Week 12. Data from Period 2 will be analyzed after all subjects have completed the study through Week 12. Data for some subjects may be collected during Period 2 after the blind has been broken.

The overall schedule of events is provided in Table 1 and the Period 1, Day -1 to Day 4 schedule of events is provided in Table 2.

Table 1. Overall Schedule of Events

Assessment	Screening D-28 to D-2	Period 1									Period 2										
		D-1	Baseline D1 (Predose)	D1	D2	D3	D4	D8	D15	D22	W8	W12 ^f									
Outpatient visit	X	Refer to Table 2: Schedule of Events for Period 1 (Day -1 to Day 4)									X	X	X		X						
Informed consent	X																				
Telephone call																				X	
Inclusion/exclusion criteria review	X																				

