- d. Continuous 12-lead ECG data will be obtained using a Mortara continuous 12-lead digital ECG recorder, with triplicate 10-second ECG recordings (approximately 1 minute apart) extracted at the following time points: Baseline (before dosing on Day 1) and at 0.5, 1, 2, 3, 4, 5, 6, 8, 12, 24, 36, 48, 60, and 72 hours after dosing.
- e. Vital signs (supine blood pressure, heart rate, respiratory rate, and oral body temperature) will be measured after the subject has rested for approximately 5 minutes.
- f. Blood samples will be collected for PK assessments at Baseline (0 hour; within 15 minutes before dosing) and at 0.5, 1, 2, 3, 4*, 5, 6, 8, 12*, 24*, 36*, 48, 60*, and 72 hours after dosing, and on Days 8, 15, and 22. (* Planned time points for analysis of moxidectin metabolite concentrations, 8-mg cohort only)

- g. Feces samples will be collected for PK assessments before dosing (single predose collection*) and each bowel motion during confinement in the clinical research unit. Samples will be pooled at the central laboratory for intervals of 0 to 24, 24 to 48, and 48 to 72 hours after dosing (up to 4 samples). (* Feces specimens [the whole bowel movement] may be collected by subjects [at home] within 2 days of submitting them to study staff on Day -1. Collection instructions will be provided at Screening.)
- h. Urine samples will be collected for PK assessments before dosing (single predose collection; first void sample in the morning is acceptable and volume recording is not required) and for pooled intervals of 0 to 24, 24 to 48, and 48 to 72 hours after dosing (4 samples).

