5.4 Pharmacokinetic/Pharmacodynamic Population

The PK/PD population will include all subjects in the ECG population who have time-matched plasma concentrations for the active moxidectin treatments. Subjects in this population will be analyzed according to the drug received (actual drug concentration).

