8.1 Continuous 12-Lead Electrocardiogram Assessments

Pharmacodynamics will be assessed via ECGs obtained using a Mortara continuous 12-lead digital ECG recorder, which will be reviewed and analyzed by the central ECG laboratory. The device will remain connected to the subject during the confinement period. The ECG data will be transmitted wirelessly to the Surveyor system, which will extract triplicate 10-second ECG recordings (approximately 1 minute apart) at baseline (before dosing) and at 0.5, 1, 2, 3, 4, 5, 6, 8, 12, 24, 36, 48, 60, and 72 hours after dosing. A window of ± 5 minutes around each time point will be utilized to capture ECGs of adequate quality, although every effort should be made to capture them as close to the scheduled time points as possible. The ECG extractions will be time-matched to the PK samples but obtained before the actual sampling time to avoid changes in autonomic tone associated with the psychological aspects of blood collection as well as the reduction in blood volume subsequent to blood collection.

The continuous ECG data will be sent to the central ECG laboratory for a high-resolution measurement of the cardiac intervals and morphological assessment. The ECG core laboratory staff will be blinded to treatment, time, and study day identifiers.

The 12-lead continuous digital ECG signal for each subject will be recorded continuously during subject confinement.

Digital ECGs will be transmitted to the central ECG laboratory's validated data management system. If targeted ECG time points are artifactual and of poor quality, the central ECG laboratory will extract analyzable 10-second ECGs as close as possible to the targeted time points. The cardiologists responsible for interpreting the ECGs will be blinded to all study drug identifiers and collection times.

Lead II is the lead of choice for the over-reads and the baseline and on-treatment ECGs will be based on the same lead. All ECGs from a particular subject will be read by a single reader.

If lead II is not analyzable, ECG analysis will be conducted in lead V₅. If lead V₅ is not analyzable, the most appropriate lead will be used (eg, lead V₂).

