  LSMEANS TRT TRT*ATPTN /DIFF ALPHA=0.1 CL;  
RUN;
```

In the above statements:

- TRT represents the treatment (active or placebo);
- ATPTN represents the postdose nominal time point;
- BASE represents the baseline value for QTcF;
- CONC represents measured plasma concentrations of moxidectin;

- SP(POW) is a spatial power law covariance structure (a time-dependent first-order autoregressive covariance designed for unequally-spaced time points), if the model does not converge then unstructured or compound symmetry structures will be assessed, in that order;
- LSMEAN differences between the treatments at the Geometric C_{\max} value and at the average concentration value, where xx.x represents the largest geometric mean C_{\max} value among the doses, most likely for the 36-mg dose, will be provided.

Model assumptions will be reviewed with plots of standardized residuals versus fitted values and normal Q-Q plots of the standardized residuals. If nonlinearity is present, a log linear and/or maximum effect (E_{\max}) or other model will be considered.

Similar analyses will be repeated for HR, PR, and QRS, however, bootstrap percentiles will be based on the 2.5th and 97.5th percentiles, corresponding to a 2-sided 95% CI rather than the 2-sided 90% CI.

Secondary Analysis: Pharmacokinetic/Pharmacodynamic Analyses

To evaluate the relationship between placebo-corrected mean change from Baseline in QTcF (ie, ddQTcF) versus plasma concentrations of moxidectin for all subjects in the PK/PD population, both graphical and mixed-effects analyses of plasma concentration of ddQTcF versus plasma concentration of moxidectin will be performed. The mixed-effects model will be used to account for the clustering effects within each subject at different time points. The mixed-effects model will contain ddQTcF as the dependent variable and include the corresponding time-matched plasma moxidectin concentrations as the independent variable. The mixed-effects model will be used to estimate, for all subjects, the predicted population mean ddQTcF and its corresponding upper 95% 1-sided (equivalent to the upper 90% 2-sided) CI over a range of observed plasma concentrations. A negative result (ie, the model indicates no plasma concentration effect) is a slope of approximately zero.

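### Does the count of 900 QTc-PK pairs in SAP Section 3.2 misstate the data behind the sample size?

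*SAP*

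**What the plan says.** Section 3.2 states that "The sample size of 60 subjects (10 subjects each in 6 treatment groups) is considered adequate" for exploring the effect of moxidectin on QTc, and gives as its reason that "this design will yield 900 QTc-PK pairs in total". It shows no derivation and states no standard deviation, assumed effect or power.

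The schedule notes in Section 3.3 list these times for the continuous ECG extractions: "Baseline (before dosing on Day 1) and at 0.5, 1, 2, 3, 4, 5, 6, 8, 12, 24, 36, 48, 60, and 72 hours after". For the plasma samples they list: "Baseline (0 hour; within 15 minutes before dosing) and at 0.5, 1, 2, 3, 4*, 5, 6, 8, 12*, 24*, 36*, 48, 60*, and 72", likewise counted from dosing. Plasma is also drawn on Days 8, 15 and 22, when there is no continuous ECG. Section 7.1 has plasma moxidectin measured in every subject. One of the six groups is "Treatment 6: matching placebo (n = 10").

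In the primary model (Section 8.3) the response is dQTcF, baseline QTcF is a covariate, placebo subjects have concentration zero, and "ATPTN represents the postdose nominal time point". The secondary ddQTcF model uses the PK/PD population, which Section 5.4 defines as "all subjects in the ECG population who have time-matched plasma concentrations for the active moxidectin treatments".

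**The concern.** The pair count is the only argument for adequacy in Section 3.2, and neither concentration-QTc model in the SAP has 900 records. The predose value is the reference for dQTcF and not a response: its change from baseline is zero by construction. Placebo records all sit at concentration zero, so they say nothing directly about the concentration slope.

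A reader who takes 900 as the analysis size would overrate the information on the slope. The reader might also overlook that the active-placebo contrast rests on 10 placebo subjects. The trial has a formal criterion, an upper 90% bound for ddQTcF below 10 msec at the largest geometric mean Cmax, and a count of pairs does not show whether 60 subjects can meet it.

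**Working it through.** **Inputs.** 60 subjects in 6 groups of 10 (Section 3.2), hence 50 on moxidectin and 10 on placebo (Section 3.3). ECG extractions are at baseline and "at 0.5, 1, 2, 3, 4, 5, 6, 8, 12, 24, 36, 48, 60, and 72 hours after dosing" (Section 8.1), that is 1 + 14 = 15 times, and the plasma schedule matches all 15.

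**Reproducing the plan's figure.** Subjects × matched times = 60 × 15 = 900, exactly. The product 50 × 18 plasma times is also 900, but 3 of those 18 times (Days 8, 15 and 22) have no continuous ECG and cannot form pairs. The other candidates fail: 60 × 14 = 840, 50 × 15 = 750, 50 × 14 = 700, 60 × 18 = 1080. The only derivation that fits the ECG schedule is therefore all subjects at all 15 times.

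**Records each model can use, as maxima.**

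| Set | Calculation | Records | Excess of 900 |
|---|---|---|---|
| Matched collections scheduled | 60 × 15 | 900 | – |
| Primary dQTcF model, postdose | 60 × 14 | 840 | 900/840 − 1 = 7.1% |
| of which placebo, concentration zero | 10 × 14 | 140 | – |
| of which moxidectin; also the secondary model | 50 × 14 | 700 | 900/700 − 1 = 28.6% |

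Missing ECGs or samples and withdrawals after dosing, which are not replaced, lower all of these.

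**What 900 against 840 is worth.** If all records were independent, the standard error would change by √(900/840) = 1.035, or 3.5%. Records are repeated within subjects. For a simple mean under a common within-subject correlation ρ, the equivalent number of independent records is Nm/(1 + (m − 1)ρ), for N subjects with m records each. The SAP gives no ρ, so 0.2 to 0.6 is assumed:

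- ρ = 0.2: 900/3.8 = 237 against 840/3.6 = 233
- ρ = 0.4: 900/6.6 = 136 against 840/6.2 = 135
- ρ = 0.6: 900/9.4 = 96 against 840/8.8 = 95

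Counting the predose time hardly matters anywhere in this range.

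**Weight of the placebo group.** Take the time-averaged active-placebo difference, with the same per-subject variance V in both arms and slope uncertainty ignored. Its variance is V/10 + V/50 = 0.12V, and placebo supplies 0.10/0.12 = 83% of it whatever V is. Precision is governed by the number of placebo subjects, which the SAP states, and not by the number of pairs.

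**The case for a change.** The strongest case for a change is that a figure offered as the reason for adequacy should describe data that an analysis will use. For the secondary model, 900 is 28.6% too high. Even a corrected count would leave the 10 msec criterion without support, so the section ought to give the expected half-width of the 90% interval at the decision concentration, with its assumed standard deviations.

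The counts behind this case stand: 840 and 700 are the right maxima. The rest is weaker:

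- The sentence refers to QTc-PK pairs yielded by the design, in total. It does not refer to dQTcF records in a model, and on that reading 900 is exact.
- The predose and placebo records are not idle. Predose QTcF is both the reference for every dQTcF and a covariate. The 140 placebo records enter the primary model and estimate the placebo time course on which ddQTcF depends.
- The size of the placebo group is not hidden. Section 3.2 gives 10 subjects per group, and Section 3.3 lists the placebo group.
- The 28.6% gap concerns the secondary analysis, for which the section makes no sizing claim.
- A half-width calculation would be additional justification and would not correct any statement in the SAP. It needs standard deviations that the SAP does not give, and a fuller sample-size rationale commonly stands in the protocol, which was not available here.

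**Conclusion.** No change is needed. The 900 pairs are a correct count of scheduled matched collections, not an arithmetic error. They are not the number of records analysed, which is at most 840 in the primary model (700 on moxidectin, 140 placebo) and at most 700 in the secondary model. Section 3.2 claims only that the size is adequate to explore the effect, and promises no power or precision that the design then misses. Replacing 900 with 840 would leave enrolment, populations, models and the 10 msec criterion as they are.

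The conclusion rests on reading the pair count as a description of what is collected, which the exact match of 60 × 15 supports. It does not establish that 60 subjects are enough for the criterion, because the SAP gives no variability from which to judge that. If the section is edited for another reason, a clause saying how many of the 900 pairs enter the primary model would be a harmless courtesy to readers.
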